8.2 Exclusion criteria

The participant may not enter the trial if any of the following apply:

- Significant infection or other acute illness, including fever > 100°F (> 37.8°C) on the day prior to or day of registration
- 2. Prognosis of less than 6 months.
- 3. ECOG Performance status of >2.
- 4. Planned receipt of any vaccine other than the **trial** intervention within 30 days before and after each **trial** intervention (day 0 and day 28) with the exception of the seasonal influenza

vaccination and non-COVID vaccinations in the case of patients receiving a haemopoietic stem cell transplant.

- 5. History of serious reactions likely to be exacerbated by any component of AZD7442 and SARS-CoV-2 vaccine.
- 6. Anaphylactic reaction following administration of a vaccine.
- 7. Known history of allergy or serious reaction to any component of the trial drugs formulation.
- 8. Patients who are pregnant or lactating at trial entry or planning to become pregnant within 3 months after AZD7442 administration.
- 9. Previous hypersensitivity, clinically significant infusion-related reaction, or severe adverse reaction following administration of a mAb.
- 10. Any prior receipt of other mAb indicated for the prevention or treatment of SARS-CoV-2 or COVID-19.
- 11. Clinically significant bleeding disorder (e.g., factor deficiency, coagulopathy, or platelet disorder), or prior history of significant bleeding or bruising following IM injections or venepuncture.
- 12. Any other significant disease, disorder, or finding that may significantly increase the risk to the participant because of participation in the trial, affect the ability of the participant to participate in the trial, or impair interpretation of the trial data.
- 13. Receipt of any IMP in the preceding 90 days or expected receipt of IMP during the period of trial follow-up, or concurrent participation in another interventional trial unless IMP is essential to clinical care*.
- 14. Blood drawn in excess of a total of 450 mL (1 unit) for any reason within 30 days prior to randomization.
- 15. A history of hypersensitivity reactions including anaphylaxis and angioedema following administration of a SARS-CoV-2 vaccine.
- 16. A history of thrombocytopenia, including immune thrombocytopenia (ITP) following administration of a SARS-CoV-2 vaccine.
- 17. A history of Guillain-Barré Syndrome.
- 18. Patients with acute promyelocytic leukaemia.
- 19. Individuals with a known history of capillary leak syndrome (CLS).

*Please notify the trial team ([contact]) of any such instances

9 Recruitment, Screening and registration

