	 12. Any other significant disease, disorder, or finding that may significantly increase the risk to the participant because of participation in the trial, affect the ability of the participant to participate in the trial, or impair interpretation of the trial data 13. Receipt of any IMP in the preceding 90 days or expected receipt of IMP during the period of trial follow-up, or concurrent participation in another interventional trial unless IMP is essential to clinical care*. 14. Blood drawn in excess of a total of 450 mL (1 unit) for any reason within 30 days prior to randomization. 15. A history of hypersensitivity reactions including anaphylaxis and angioedema following administration of a COVID-19 vaccine 16. A history of thrombocytopenia, including immune thrombocytopenia (ITP) following administration of a COVID-19 vaccine 17. A history of Guillain-Barré Syndrome 18. Patients with acute promyelocytic leukaemia 19. Individuals with a known history of capillary leak syndrome (CLS). 	
Treatment duration	28 days	
Follow-up duration	6 months	
Planned trial period	9 months	
Primary objectives	 a. To assess the pharmacokinetics of AZD7442 administered as a single dose of 600 mg IM in immunosuppressed patients b. To assess the safety and tolerability of a single IM dose of AZD7442, followed by SARS-CoV2 vaccine booster 28 days later with reference to serious adverse events (SAEs) in highly vulnerable patients. c. To assess the SARS-CoV-2 specific humoral and cellular immune response against SARS-CoV-2 variants, when a SARS-CoV-2 vaccine is administered 28 days after AZD7442 in patients who are immune suppressed. d. To assess the effect of a SARS-CoV-2 vaccine on AZD7442 monoclonal antibody titres e. To assess neutralizing antibodies to SARS-CoV-2 using validated wild-type neutralization assay or pseudo-neutralization assays over time. 	
Secondary objectives	 a. The incidence of participants who have a post-treatment response (negative/low at baseline to positive at any time post-baseline) for SARS-CoV-2 nucleocapsid antibodies. b. The incidence of SARS-CoV-2 infection in trial participants. c. Sequencing of confirmed SARS-CoV2 infections to identify SARS-CoV2 	

	d. To assess the behaviour of the trial participants before and after trial treatment.	
	e. To assess if different SARS-CoV-2 vaccines will preferentially enhance humoral and/or T cell responses in immune suppressed patients receiving AZD7442.	

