3.2 Trial lay summary

Despite repeated vaccinations against COVID-19, some people with impaired immune systems caused by cancer and its treatment, inflammatory conditions, and those with organ transplants and other serious health conditions remain at very high risk of catching COVID-19 and becoming unwell.

AZD7442 (Evusheld) is a long-acting antibody treatment which has been shown in clinical trials to prevent COVID-19 infection for up to a year after a single dose. AZD7442 has been approved for use in the United States for the prevention of COVID-19 and in the UK to prevent COVID-19.

Vaccines require a healthy immune system to generate protective immunity. AZD7442 may prevent COVID-19 in people with impaired immune systems that may not have responded to repeated vaccinations against COVID-19. Unlike vaccinations, which take several doses given weeks apart to reach maximum efficacy, AZD7442 reaches effective levels within the body a few hours after a single dose.

The RAPID-PROTECTION trial will determine the levels of immune protection that AZD7442 offers patients at the very highest risk of COVID-19 infection using laboratory-based tests and whether or not this protection can be further enhanced by repeated vaccination against COVID-19. It is an adaptive platform which will allow increased recruitment in sub-groups of greatest uncertainty of effect.

All the participants in the trial will receive AZD7442 and then 28 days later a COVID-19 vaccination with either the Moderna vaccine or Pfizer/BioNTech vaccine that have been approved for use in the UK. All the participants and their trial teams will know which treatment and vaccines they have been offered in the trial. All the participants will have blood tests before, during and after each trial treatment to check the levels of AZD7442 and to examine their immune responses against COVID-19. Unless the study team specifically advise otherwise, participants will not be able to receive any of the approved NHS COVID-19 vaccines for three months after receiving their booster vaccine within the trial.

4. Background

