- All AEs reported were mild in intensity, with the exception of the following events of moderate intensity: urinary tract infection (1 subject) in Cohort 1a; headache, malaise (1 subject each) and urinary tract infection (1 subject) in Cohort 1b; dysmenorrhea and headache (1 subject each) and toothache (2 participants) in Cohort 2; headache, back pain, and arthralgia (1 subject each) in Cohort 3; and back pain (1 subject) in Cohort 4.
- There were no haematology, clinical chemistry, or vital signs findings of concern in any subject.

In addition, by Day 211, no participants in the study tested positive for ADA to either AZD8895 or AZD1061. Since ADA-positive to AZD7442 is defined as having a positive result to AZD8895 and/or AZD1061, no participants tested positive for ADA to AZD7442. Thus, both ADA prevalence (percentage

ARDIF

of ADA-positive participants in the study) and ADA incidence (percentage of treatment-emergent ADApositive participants in the study) were 0%. The serum AZD8895 and AZD1061 concentrations observed in the Phase I study support that the PK of the 2 antibodies are similar. The half-life of AZD7442 is estimated to be ~ 90 days which will allow for long-term protection. Overall, the Cmax and AUC increased linearly with increasing IV dose. Administering AZD8895 and AZD1061 separately or together did not alter the PK of the mAbs as indicated by the overlapping serum drug concentrationtime curves. In addition, key exposure PK parameters such as AUC and Cmax for AZD8895 and AZD1061 were similar between the 2 dosing regimens.

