10.2 Lost to follow up

Participants who withdraw from the trial or cease to attend trial visits prior to the end of the followup period will be classed as lost to follow up.

Every effort will be made to obtain follow-up information on these patients, unless they have completely withdrawn from the trial. Participants who are not present for a scheduled visit or follow up will be contacted by their local research team by telephone or letter. If they are contactable, the local research team will ask them to make an appointment to be seen at the next available clinic. If the participant declines or cannot be contacted, the local research team will inform their GP. If the participant is alive but not compliant with the approved visit schedule, the minimum information the local research team will aim to collect is the day 28 blood sample and visit assessment.

11 Trial Intervention

The following treatments are considered as IMPs within this trial:

- AZD7442 (Combination Monoclonal Antibody Product)
- Comirnaty bivalent (Original/Omicron BA.1) (Pfizer BioNTech)
- Spikevax bivalent (Original/Omicron) (Moderna)

Comirnaty bivalent Original/Omicron BA.1 and Spikevax bivalent (Original/Omicron)vaccines are approved for use under a conditional marketing authorisation of the supply of an unlicensed vaccine; regulation 174 of the Human Medicines Regulations 2012. Both vaccines will either be obtained through local supply or ordered from the UK Health Security Agency via the clinical trials unit. The initial supply of the vaccines will be triggered by the clinical trials unit upon receipt of all necessary approvals for the site. To order further vaccines, please contact [contact].

There is no requirement for the vaccines to be labelled as IMP for this trial. Vaccine accountability will be in accordance with local Trust policy. Vaccine should be stored and prepared as specified in the Information for UK Healthcare Professionals. See the RAPID-PROTECTION Pharmacy Manual for additional information.

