11.6 Permitted, Restricted, and Prohibited Medications

Permitted, restricted, and prohibited medications are summarized in Table 5. Any medication or vaccine (including over-the-counter or prescription medicines, vitamins, and/or herbal supplements) that the participant is receiving at the time of enrolment or receives during the trial must be recorded, along with:

- Reason for use
- Dates of administration, including start and end dates
- Dosage information, including dose and frequency

The Trial Physician should be contacted if there are any questions regarding concomitant or prior therapy

Use Category	Type of medication/treatment	Timeline/instructions
Permitted	Routine Vaccines	Licensed influenza vaccines are permitted at any time. All other routine non-COVID vaccines are permitted beginning > 30 days after IMP dose with the exception of patients receiving a haemopoietic stem cell transplant who may receive non-COVID vaccines at any time.
	Allergen immunotherapy	Allowed if participant has been receiving stable therapy for at least 30 days prior to Visit 1 and there is no anticipated change during the treatment period. Allergen immunotherapy should not be administered on the same day as IMP

Table 5: Permitted, restricted and prohibited medications

Centre for Trials Research Canolfan

	Commercial biologics,	Allowed, provided the
	prednisone,	participant is stable on
	immunosuppressive	maintenance dose (at steady
	medications (e.g., azathioprine,	state) prior to Visit 1, and must
	tacrolimus, cyclosporine,	not be administered on the
	methotrexate, or cytotoxic	same day as IMP
	chemotherapy,	
	immunotherapy or targeted	
	treatment for cancer)	
		tant medications prescribed by
		ospital team for management of nd/or for health maintenance.
		hospital providers, or where
		hould prescribe appropriate
		eatments deemed necessary to
		and comfort during the trial.
		-19 after receiving IMP should be
	treated according to local	standard of care, including
	investigational agents within a c	linical trial setting.
Prohibited	Not applicable	Not applicable
Restricted	Contraceptive methods	See section 14.8
	Blood/plasma donation	Participants must abstain from
		donating blood or plasma from
		the time of informed consent
		and for 5 half-lives after dose of
		study drug, i.e. one year.
	Standard of care COVID-19	Participants must not obtain
	vaccines	standard of care approved
		COVID-19 boosters until at
		least 3 months after receiving

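### Exclusion 10 bars only *other* anti-SARS-CoV-2 antibodies, so prior AZD7442 is not expressly excluded from a trial with a co-primary single-dose PK objective

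*Protocol*

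**What the plan says.** Exclusion 10 in section 8.2, with the same wording in the synopsis, bars "Any prior receipt of other mAb indicated for the prevention or treatment of SARS-CoV-2 or COVID-19". Two neighbouring criteria could bear on earlier AZD7442:

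- Exclusion 13: "Receipt of any IMP in the preceding 90 days or expected receipt of IMP during the period of trial follow-up". It ends with an exception for an IMP that is essential to clinical care.
- Exclusion 12: a general clause on any significant disease, disorder or finding that may raise risk, affect participation "or impair interpretation of the trial data".

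The lay summary (section 3.2) says that "AZD7442 has been approved for use in the United States for the prevention of COVID-19 and in the UK to prevent COVID-19". Section 9.1 allows patients from previous related studies to be approached. On persistence, section 4.6 says: "The half-life of AZD7442 is estimated to be ~ 90 days which will allow for long-term protection". It also reports that the Phase I 300 mg cohorts kept a 4-fold rise in neutralising titre to Day 271. The blood-donation restriction in section 11.6 runs from consent "and for 5 half-lives after dose of" study drug, which it equates with one year.

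The first co-primary objective is "To assess the pharmacokinetics of AZD7442 administered as a single dose of 600 mg IM in immunosuppressed patients". Table 1 schedules a pre-dose PK sample at Day 0, then samples at Days 28, 112 and 180. Section 16.1.1 judges the immunological effect against baseline and compares each cohort with PROVENT. Section 15.7 places every enrolled participant in the analyses.

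**The concern.** Taken as written, the criteria let someone treated with AZD7442 some months earlier enrol with drug still circulating. The protocol makes this foreseeable: the product is approved in the UK, and the trial seeks the patients most likely to benefit from it.

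For such a participant:

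- The PK profile is the sum of two doses, although the objective concerns one.
- The Day 0 anti-spike and neutralising titres are raised, so the rise from baseline is understated.
- Later titres are raised too. The tests against PROVENT in section 16.1.1 are one-sided, looking for trial patients doing worse, so residual drug works against finding what they look for.
- Mixing previously treated and untreated people changes the within-cohort variance, which section 15.3 uses to decide whether to go on to the individual groups.

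**Working it through.** The protocol states no figure for carry-over, so there is none to reproduce. The check has two parts.

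**Do the other criteria close the gap?**

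- Exclusion 13 catches AZD7442 given as an IMP in another trial within 90 days. Section 11 lists AZD7442 among this trial's IMPs, so it may also catch any AZD7442 within 90 days. Whether it reaches routine-care use is unclear, and on either reading it lapses after 90 days.
- Exclusion 12 could be applied by an investigator who knows of the earlier dose, but it is discretionary and worded around disease or findings.
- The baseline medication review (section 13.1) looks back 28 days, and the SARS-CoV-2 history form concerns vaccines. Older AZD7442 would surface only through the general history or the notes.

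**How much drug could remain?**

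Inputs: half-life of about 90 days (section 4.6), trial dose 600 mg (section 11.1). Assumptions: first-order elimination, and the same absorption for both doses.

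Fraction of the earlier dose left after t days = 0.5^(t/90). Excess over the trial dose alone = (earlier dose / 600) × that fraction. Old and new drug decay at the same rate, so the percentage excess stays the same at later visits.

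| Days since earlier dose | Fraction left | Excess, earlier 300 mg | Excess, earlier 600 mg |
|---|---|---|---|
| 90 | 0.500 | 25.0% | 50.0% |
| 180 | 0.250 | 12.5% | 25.0% |
| 270 | 0.125 | 6.2% | 12.5% |
| 365 | 0.060 | 3.0% | 6.0% |

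Sensitivity to the half-life: 73 days is the value at which five half-lives equal 365 days (365/5), and 110 days is an assumed upper value. Over that range, 43–57% of the earlier dose remains at 90 days and 18–32% at 180 days. When the exclusion 13 window ends, roughly half of an earlier dose can still be present.

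**Effect on a group mean.** Bias in the mean concentration ≈ share of participants affected × their excess. The share is not in the protocol, so these are assumptions:

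- none affected: 0
- 2% affected, excess 12.5–50%: 0.02 × 12.5% = 0.25% to 0.02 × 50% = 1%
- 5–20% affected, excess 12.5–50%: 0.05 × 12.5% ≈ 0.6% to 0.20 × 50% = 10%

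**Titres.** A 4-fold raised baseline is log10(4) = 0.60, or ln(4) = 1.39. Either exceeds the 0.5 log-domain difference used for planning in section 15.3. This describes one participant, not a group mean, and the Phase I volunteers were healthy, so the fold-rise in vaccinated patients may differ.

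**The case against.** The strongest reply is that the problem may be nearly empty. UK approval does not show that UK patients were being supplied, and Table 2 lists the product's use here as experimental. PROVENT enrolled unvaccinated people, few of them at highest risk, so earlier trials are a thin source of previously treated participants. Exclusions 12 and 13 offer two routes to keep them out, and inclusion 5 gives access to past treatment records. The Day 0 pre-dose sample would reveal residual drug. Section 16.1.5 leaves PK methods to the SAP, where pre-dose concentrations are commonly dealt with.

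Much of this stands. The number affected is unknown, the other criteria help, and the problem is detectable. It does not remove the point: criteria that may or may not cover prior AZD7442 leave each site to decide, and 90 days is too short to ensure a drug-free baseline by the protocol's own half-life.

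A reader might infer more than the documents support:

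- *That exclusion 13 is the only other barrier.* Exclusion 12 is a second one, though discretionary.
- *That concentrations will be 12–50% too high.* Those are four chosen scenarios for an affected individual. Longer intervals give less; shorter ones, if admitted, give more.
- *That the vaccine comparison is biased.* Allocation is 1:1 at random and section 16.1.2 adjusts for baseline, so a few previously treated participants would not bias it systematically.
- *That all immune endpoints are affected.* An anti-spike antibody does not directly raise nucleocapsid antibodies or T-cell measures.
- *That section 15.7 proves no PK rule exists.* The SAP is not available. The point is only that a rule omitting participants would conflict with section 15.7 as worded.

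**Conclusion.** The gap is real and should be corrected. Prior AZD7442 is not expressly excluded, and the criteria that might catch it do so incompletely. For a previously treated participant, the excess over the single-dose concentration is about 12.5–25% after an earlier 300 mg and 25–50% after an earlier 600 mg, for intervals of 180 and 90 days respectively. This assumes a 90-day half-life, linear elimination and equal absorption. The effect on group results depends on a share that the protocol does not give and may be negligible.

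The exposed analyses are the co-primary single-dose PK summary and the anti-spike and neutralising comparisons with baseline and with PROVENT. Because recruitment was paused in April 2023 (section 13.1.1), the eligibility wording matters only if it resumes; handling of those already enrolled matters now.

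**What to change.** 1. Delete *other* from exclusion 10 in section 8.2 and in the synopsis, in case recruitment resumes, and reconcile it with exclusion 13 so that the two give one answer on prior AZD7442. No wash-out interval is proposed here.
2. Qualify section 15.7 so that the single-dose PK summary omits participants with documented prior AZD7442 or a non-trivial Day 0 pre-dose concentration, for example above 5% of their own Day 28 value. With a 90-day half-life, Day 28 retains 0.5^(28/90) = 0.806 of the starting level. If x is the excess, the 5% limit solves x / [0.806 × (1 + x)] = 0.05, so x ≈ 0.042. The rule would flag an excess above about 4%, which covers the 90- and 180-day scenarios, and it ignores trivial residues.
3. Keep all participants in the main anti-spike and neutralising analyses and repeat these without the flagged participants as a sensitivity analysis. Dropping everyone with any quantifiable Day 0 drug from the main analysis would be broader than needed.
4. Keep them in all safety analyses.

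Cost: a one-word amendment in two places and one analysis rule. The Day 0 sample is already scheduled, although the protocol does not show whether it has been assayed. A few participants may leave the PK summary.

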9.1 Participant identification and screening

Highly immunocompromised patients may be identified by the recruiting sites through their clinical treatment team and multidisciplinary team. Additional patients can be identified by the research nurse from the patient notes. Participants may also be referred through their GPs and secondary care providers to participating sites. Similarly, patients involved in previous related studies may be approached by their treating team. Once patients have been identified as potentially suitable, patients

will be approached by a healthcare professional responsible for their clinical care for a referral to the site study team. The decision to accept this referral ultimately lies with each participating site.

The Eligibility Checklist should be completed prior to randomisation by the Investigator or clinical designee listed on the trial delegation log and recorded in the patient notes. This will include a pregnancy test for women who are of child-bearing potential.

Individuals being screened may or may not be eligible to receive a SARS-CoV2 vaccine booster as part of standard care at the time of being approached for the trial or during the trial. Scheduling of AZD7442 treatment may need to be considered should individuals being screened for the trial be due a SARS-CoV2 vaccine booster as part standard of care, to ensure they are given AZD7442 treatment at least 28 days after receiving the standard of care booster.

9.2 Screening logs

A screening log of all ineligible and eligible but not consented will be kept at each site so that any biases from differential recruitment will be detected. Separate screening logs will be used for each cohort at each site. When at site, logs may contain identifiable information, but this must be redacted prior to being sent to the CTR. The screening log should be sent to the [contact] every 2 weeks (see section 23 for further detail on data monitoring/quality assurance).

